Quasi-Randomized Evaluation of the UCLA Next Day Clinic (NDC)

NCT ID: 24-000913

Updated 08/15/2024

Statistical analysis. For the primary analysis, we will compare DAOH between eligible patients in the treatment and control arms as-randomized using an instrumental variable (IV) analysis, with encouragement to refer (even/odd birth date) as the binary instrumental variable and treatment setting (NDC v. inpatient) as the exposure. Analysis will utilize a two-stage least squares approach. In the first stage, we will regress treatment setting on the instrument and all covariates. In the second stage, we will use predicted values of treatment setting to estimate differences in DAOH between arms, adjusting for the same covariates. This procedure will be repeated for the secondary outcomes of global health-related quality of life, patient experience, and the financial analysis. Covariates will include: diagnosis, comorbidity score, age, sex, insurance type, zip code, and race/ ethnicity. We will use heteroskedasticity-robust standard errors. We will evaluate the NDC's impact on health disparities by performing subgroup analyses across racial/ethnic, sex, age, and socioeconomic lines, ensuring outcomes do not differ and that all groups have equitable access to the NDC.

We will perform the following three secondary analyses:

- 1) Subset analysis to define a specific subgroup of patients based on the probability of being referred to the NDC. Specifically, we will use a logistic regression based on patient labs, vitals, characteristics, and comorbidities to estimate the probability of referral to NDC, and use a median split to define a threshold. We will then apply this threshold to the control group, and repeat the primary analysis of treatment v. control group only including patients above the pre-specified threshold.
- 2) Per-protocol analysis of eligible patients repeating the primary analysis methodology but only among patients who adhered to the assignment and treatment protocol.
- 3) Difference-in-differences (DiD) analysis using UCLA Santa Monica Medical Center as a control. We will compare 30-day DAOH among the eligible cohort at Ronald Reagan UCLA Medical Center to a matched eligible cohort at UCLA Santa Monica Medical Center (cohorts will be constructed using the same logic and rules). The dependent variable will be 30-day DAOH, the independent variables will be hospital location, intervention period, location x intervention interaction, and the above specified covariates.

We will also perform a formal cost-effectiveness analysis (CEA) using standard CEA methodologies to measure the incremental cost-effectiveness ratio (ICER).

For the patient-reported secondary outcomes, we will perform a complete case analysis as the primary analysis, but as a sensitivity analysis we will estimate the probability of responding to the survey using a logistic regression model informed by baseline patient characteristics, and do an inverse probability-weighted analysis to correct for non-response.

Sample size and power. Based on historical UCLA data, we expect 850 patients to be randomized in a 12-month period. Assuming similar numbers during this trial, a 1:1 randomization by birthdate would trigger the encouragement 425 times. On an as-randomized basis, two groups of 425 patients would provide 80% power to detect an effect size as small as 0.192 standard deviations (SDs) on our primary outcome, DAOH, assuming a two-sample t-test and a two-sided 0.05 significance level. If ED physicians and patients accept the 425

encouragements 50% of the time in the treatment group and there is 10% contamination in the control group (i.e., 10% of eligible patients randomized to control get referred to the NDC), then the delta effect of the instrument on referral will be 40%. Thus, the IV parameter will be $0.192 / 0.40 = 0.48$ SDs. In the historical sample, mean DAOH was 26.8 with a SD of 2.2 days. We will therefore have 80% power to detect an IV effect of referral to the NDC of $2.2 * 0.48 = 1.1$ days.

In this quality improvement project funded by the health system, the health system may terminate the study early at their own discretion. Should this happen, analysis will commence with the sample size enrolled at the time of termination. If this happens we will conduct a conditional power analysis to evaluate how much power we would have based on the sample size at the time of trial termination. Similarly, we will also determine power conditional on actual rates of referral to the NDC (e.g., if referral rates are below the above specified 50%, or if contamination rates are above the above specified 10%).

Additional eligibility criteria specifications:

ALL THREE CRITERION MUST BE MET FOR PATIENT TO BE NDC-ELIGIBLE (in addition to the inclusion/exclusion criteria in the NCT documentation).

Criterion #1: Patient has even birth date (e.g., December 2nd, 4th, 6th).

Criterion #2: All of the following clinical criteria are met (using most recent labs/vitals):

- Sodium between 129-150
- Potassium between 2.9-5.9
- WBC \leq 16k
- O2 sat \geq 89%
- Heart rate between 50-110
- Respiratory rate $<$ 30
- Systolic blood pressure between 90-190

Criterion #3: Plan to Admit order placed with one of the following ICD-10 codes:

Cellulitis

- ICD-10 wildcards
 - L01, L02, L03, L04, L05, L98
- ICD-10 exact matches
 - L00, L08.89, L08.9, L30.3, H60.10, K12.2, N73.0, N73.1, N73.2, T14.8XXA, I96
- SmartSets to suggest to ED providers
 - NDC Cellulitis
 - NDC Diabetic foot/osteomyelitis

Diabetic foot infection

- ICD-10 wildcards
 - E10.62, E11.62
- ICD-10 exact matches

- E10.610, E11.610
- SmartSets to suggest to ED providers
 - NDC Diabetic foot/osteomyelitis

Osteomyelitis

- ICD-10 wildcards
 - M46.2, M46.3, M46.4, M46.5
- ICD-10 exact matches
 - M46.1
- SmartSets to suggest to ED providers
 - NDC Cellulitis
 - NDC Diabetic foot/osteomyelitis

Syncope

- ICD-10 wildcards
 - T67.1
- ICD-10 exact matches
 - R55, R42, R05.4, G90.01
- SmartSets to suggest to ED providers
 - NDC Syncope

AKI

- ICD-10 wildcards
 - N17, S37.00
- ICD-10 exact matches
 - N19
- SmartSets to suggest to ED providers
 - NDC AKI

CKD

- ICD-10 wildcards
 - N18.3
- ICD-10 exact matches
 - N18.1, N18.2, N18.4, N18.9
- SmartSets to suggest to ED providers
 - NDC AKI

CHF

- ICD-10 wildcards
 - I50, I42, I13, I11, E87.7
- ICD-10 exact matches
 - I09.81, I25.5

- SmartSets to suggest to ED providers
 - NDC CHF

Pyelonephritis

- ICD-10 wildcards
 - N10
- ICD-10 exact matches
 - A02.25
- SmartSets to suggest to ED providers
 - NDC Pyelonephritis/UTI

Acute cystitis

- ICD-10 wildcards
 - N30
- ICD-10 exact matches
 - N34.1, N34.2, N34.3, R30.0, R30.9, R82.71, R82.81
- SmartSets to suggest to ED providers
 - NDC Pyelonephritis/UTI

Hematuria

- ICD-10 wildcards
 - R31
- ICD-10 exact matches
 - R82.3
- SmartSets to suggest to ED providers
 - NDC Pyelonephritis/UTI

Pneumonia

- ICD-10 wildcards
 - J12, J14, J15, J16, J18, J22
- ICD-10 exact matches
 - A01.03, A02.22, A21.2, A22.1, A31.0, A37.11, A37.91, A41.0, A43.0, A48.1, A54.84, A70
- SmartSets to suggest to ED providers
 - NDC Pneumonia

Dyspnea

- ICD-10 wildcards
 - R06
- ICD-10 exact matches
 - None 
- SmartSets to suggest to ED

- NDC Pneumonia
- NDC CHF

Obstructive lung disease

- ICD-10 wildcards
 - J20, J40, J41, J42, J43, J47, J98
- ICD-10 exact matches
 - J44.0, J44.1, J44.9
- SmartSets to suggest to ED
 - NDC Pneumonia
 - NDC CHF

Dehydration

- ICD-10 wildcards
 - E86
- ICD-10 exact matches
 - None!
- SmartSets to suggest to ED providers
 - NDC AKI

Urinary retention

- ICD-10 wildcards
 - R33, N40
- ICD-10 exact matches
 - None!
- SmartSets to suggest to ED providers
 - NDC AKI

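### Does leaving the coding of zip code unstated put the two-stage least squares analysis at risk?

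*SAP*

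**What the plan says.** In the SAP's Statistical analysis section, the primary comparison of DAOH uses two-stage least squares, with birth date parity as the instrument and treatment setting as the exposure. The list reads "Covariates will include: diagnosis, comorbidity score, age, sex, insurance type, zip code", followed by race/ethnicity. It enters both stages; for the first, "In the first stage, we will regress treatment setting on the instrument and all covariates". On inference the section adds "We will use heteroskedasticity-robust standard errors", with no mention of a degrees-of-freedom correction.

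The list is reused for the secondary outcomes, for the median-split subset ("repeat the primary analysis of treatment v. control group only including patients above the pre-specified threshold") and for the difference-in-differences model ("location x intervention interaction, and the above specified covariates"). Subgroups are planned by "performing subgroup analyses across racial/ethnic, sex, age, and socioeconomic lines", without naming a socioeconomic variable.

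The Sample size and power section works "assuming a two-sample t-test and a two-sided 0.05 significance level", so it makes no allowance for covariates in either direction. If the health system stops the study early, "analysis will commence with the sample size enrolled at the time of termination", with a conditional power analysis at that size.

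**The concern.** Zip code is a label that can take many values and has no natural numeric scale, so two analysts following the text could fit different models. Entered as a number, its slope means nothing. Entered as one indicator per code, it confines the comparison to patients who share a code: some of the even/odd variation is lost, and a patient alone in a code adds nothing.

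At stake would be precision in the primary analysis, and more of it in the median-split subset or after an early stop, where there are fewer patients per code. With very many indicators, an uncorrected robust standard error is also somewhat too small. One continuous zip-level income term would avoid all of this at a cost of one or two degrees of freedom, and could also serve the socioeconomic subgroup.

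**Working it through.** **1. The plan's own figures.** Inputs from Sample size and power: 850 patients, 425 per arm, 0.192 SD, two-sided 0.05, uptake 50% v. 10%, SD 2.2 days.

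- Two-sample t power at 0.192 SD with 425 per arm: 79.8%, stated as 80%.
- 0.50 − 0.10 = 0.40; 0.192 / 0.40 = 0.48 SD; 2.2 × 0.48 = 1.056 days, stated as 1.1.

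These reproduce.

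**2. One indicator per code.** The number of codes k is an assumption. The expected share of even/odd variation left is (850 − k)/850. The standard error is multiplied by √(850/(850 − k)), and the detectable effect is 1.056 times that factor. Power is the t-test power at 0.192 SD with 850 − k patients. These figures suppose that the codes explain none of DAOH; the loss cancels if they explain k/850 of its variance.

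| k | share left | SE factor | detectable (days) | power | break-even |
|---|---|---|---|---|---|
| 20 | 0.976 | 1.01 | 1.069 | 78.9% | 2.4% |
| 50 | 0.941 | 1.03 | 1.088 | 77.4% | 5.9% |
| 100 | 0.882 | 1.06 | 1.124 | 74.7% | 11.8% |
| 200 | 0.765 | 1.14 | 1.208 | 68.6% | 23.5% |

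The detectable effect still rounds to 1.1 while it is below 1.15 days: 850 × (1 − (1.056/1.15)²) ≈ 133, so up to about 130 codes.

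**3. The codings compared on the same data.** Two-stage least squares was simulated at the plan's inputs (850 patients, 50% v. 10% uptake, SD 2.2, effect 1.056 days, uneven zip sizes, 6,000 runs per cell, Monte Carlo error about 0.5 points). Robust standard errors were degrees-of-freedom corrected. Power in % at 20 / 50 / 100 / 200 codes:

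| DAOH variance explained by codes | numeric zip | one area score | indicators |
|---|---|---|---|
| 0% | 79.2 / 79.6 / 78.6 / 80.8 | 79.2 / 79.6 / 78.6 / 80.9 | 78.4 / 77.2 / 73.1 / 66.5 |
| 5%, all through the score | 79.8 / 78.1 / 79.6 / 80.0 | 81.4 / 80.0 / 81.5 / 82.0 | 80.4 / 77.8 / 75.8 / 68.1 |
| 5%, half through the score | not tabulated | 79.5 / 80.1 / 80.2 / 80.4 | 79.2 / 78.5 / 76.4 / 67.9 |
| 10%, half through the score | not tabulated | 81.3 / 80.8 / 82.2 / 81.1 | 82.2 / 80.9 / 78.3 / 69.8 |

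Mean estimates were 1.04 to 1.06 days in every cell, so no coding is biased. Numeric zip matches the score when the codes do not predict DAOH, and is about 2 points behind when they explain 5% wholly through the score. With 10% explained, indicators are slightly ahead at 20 codes and level at 50.

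**4. Type I error.** In 20,000 runs, indicators with an uncorrected robust standard error gave 5.1%, 5.4%, 6.0% and 7.1%. With the correction they gave 4.7%, 4.7%, 4.3% and 3.9%, against 4.7%, 4.8%, 4.5% and 5.0% for the score. The corrected indicator test is therefore conservative at many codes, and part of the gap in step 3 is test level rather than coding. By a normal approximation, at 200 codes a level of 3.9% means a critical value of 2.064, so power at a true 5% level is Φ(Φ⁻¹(0.665) + 2.064 − 1.960) ≈ 70%. At 100 codes it is Φ(Φ⁻¹(0.731) + 2.024 − 1.960) ≈ 75%. Both are close to the closed-form figures in step 2.

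**5. Half the sample.** In a random half of 425, about 20, 48, 91 and 162 of the codes remain. The standard error factors √(425/(425 − k)) are 1.02, 1.06, 1.13 and 1.27, and uncorrected type I error is 4.9%, 5.8%, 6.9% and 7.9%.

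**The case for a change.** The best case for a change is that fixing a covariate's form is the SAP's own job, that this list feeds the primary model and most of the others, and that the repair is one phrase and a lookup merge. It would protect against a loss of roughly 5 to 11 points of power at 100 to 200 codes, and against a mildly liberal test if the robust standard error is left uncorrected. The exposure is greater in the subset and after an early stop.

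What stands is that the coding is not stated, and that indicators for 100 or more weakly predictive codes would be a poor choice. The rest does not carry:

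- The loss needs indicator coding and many codes together, and the SAP states neither.
- The meaningless slope does no harm, because zip code is an adjustment variable and its coefficient is not among the results the plan sets out.
- Area income is one option among several. A deprivation index or a few grouped areas would also avoid the loss, and income drops distance and access, which the SAP may equally have had in mind.
- The income term would not settle the socioeconomic subgroup without a cut-point or interaction form. Nor would it settle the difference-in-differences model, where hospital is not randomized and location may matter more.
- Diagnosis, insurance type, race/ethnicity, age and comorbidity score are listed just as briefly.
- For an early stop, the plan already provides a conditional power analysis at the sample size reached.

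**Conclusion.** No change follows. The plan names its adjustment variables and leaves the coding of one of them to the analyst, and following it as written still gives a sound result. No stated figure is wrong and no coding biases the estimate. At 50 or fewer codes the cost of indicators is about 3% in standard error and at most about 2.4 points of power. It reaches about 5 points at 100 codes and 11 at 200 only if indicators are used and the codes explain little of DAOH. Numeric coding costs nothing against leaving zip code out.

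The choice between indicators, a numeric term and an area measure is a fair trade-off between finer geographic adjustment and precision, and its balance depends on a number of codes that the document does not give. An analyst who finds many sparsely filled codes would ordinarily group them or use an area measure, and would correct the robust standard error if indicators were kept.

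These sizes rest on the plan's inputs, on the assumed range of 20 to 200 codes, on uneven zip sizes in the simulation, and on codes explaining 0% to 10% of DAOH variance.

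### The covariate list for the two-stage least squares and difference-in-differences models leaves out the seven labs and vitals that Criterion #2 already requires; the primary analysis loses some efficiency, probably little, and the DiD cannot adjust for acuity within the eligible ranges

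*SAP*

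**What the plan says.** The covariates for the primary analysis are in the SAP's Statistical analysis section: "Covariates will include: diagnosis, comorbidity score, age, sex, insurance type, zip code, and race/ ethnicity". They enter both stages; for the first, "In the first stage, we will regress treatment setting on the instrument and all covariates", and the second adjusts for the same set. The procedure is repeated for the secondary outcomes. The DiD (secondary analysis 3) takes hospital location, intervention period, "location x intervention interaction, and the above specified covariates".

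Labs and vitals appear in two other places:

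- Additional eligibility criteria specifications: "Criterion #2: All of the following clinical criteria are met (using most recent labs/vitals"). Seven values follow: sodium, potassium, WBC, O2 saturation, heart rate, respiratory rate and systolic pressure.
- Secondary analysis 1: "we will use a logistic regression based on patient labs, vitals, characteristics, and comorbidities to estimate the probability of referral to NDC".

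The SAP gives no reason for leaving these values out of the outcome models.

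**The concern.** The eligible ranges are wide (for example heart rate 50 to 110, O2 saturation from 89%, respiratory rate below 30), so patients can differ in severity within them. That severity plausibly predicts length of stay and readmission, and so DAOH. Diagnosis and comorbidity score describe what the patient has. They do not describe how ill the patient is on presentation.

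The stakes differ between the two models.

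- **Primary IV.** A baseline variable that predicts DAOH reduces residual variance. Any gain on the as-randomized scale carries over to the IV scale, where the detectable effect is divided by 0.40. The SAP also foresees early termination and weaker referral than planned, and in either case precision would be worth more.
- **DiD.** Hospital and period are not randomised. A change in acuity that differs between the two hospitals over time would be read as an effect of the clinic, and nothing in the list measures it.

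**Working it through.** **Inputs (SAP, Sample size and power).** 425 patients per arm (850 in total); 80% power; two-sided 0.05; unadjusted two-sample t-test; 0.192 SD detectable as-randomized; referral 50% v. 10%, a difference of 0.40; SD of DAOH 2.2 days.

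**Reproducing the plan's figure.** (1.96 + 0.84) × sqrt(2/425) = 0.192 SD. On the IV scale, 0.192/0.40 = 0.48 SD, and 0.48 × 2.2 = 1.056 days, which the SAP rounds to 1.1. The figure reproduces.

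**Effect of adding the seven values.** Let r be the share of DAOH variance that they explain beyond the listed covariates. The documents do not give r, so it is an assumed range.

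- Detectable IV effect = 1.056 × sqrt(1 − r)
- Power at 1.056 days = Φ(2.80/sqrt(1 − r) − 1.96)
- Equivalent extra patients = 850 × (1/(1 − r) − 1)

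| r (assumed) | Detectable IV effect (days) | Power at 1.06 days | Equivalent extra patients |
|---|---|---|---|
| 0 | 1.06 | 80% | 0 |
| 0.02 | 1.05 | 81% | 17 |
| 0.05 | 1.03 | 82% | 45 |
| 0.10 | 1.00 | 84% | 94 |
| 0.15 | 0.97 | 86% | 150 |

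The table keeps the plan's unadjusted SD of 2.2 days as its base. If the listed covariates already reduce that SD, the base is smaller, but the ratio sqrt(1 − r) is unchanged.

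**Cost if the values explain nothing.** Seven extra coefficients inflate the standard error by sqrt(848/841) = 1.004, about 0.4%. Fourteen give sqrt(848/834) = 1.008, about 0.8%.

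**Simulation check.** Just-identified two-stage least squares with robust standard errors, N = 850, 3,000 replicates per setting, with severity also influencing referral. Power without v. with the seven values:

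- r = 0: 79.1% v. 77.7%
- r = 0.02: 79.6% v. 79.4%
- r = 0.05: 79.9% v. 81.0%
- r = 0.10: 79.4% v. 82.1%

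Each power figure has a Monte Carlo standard error of about sqrt(0.8 × 0.2/3000) = 0.7 points, so differences at r of 0.05 or less are hardly distinguishable from noise. The mean IV estimate was 1.05 to 1.06 days in every setting, with or without adjustment, against a true value of 1.056. Leaving the values out caused no bias.

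**DiD.** The location term absorbs a stable difference between hospitals, and the period term absorbs a common trend. What remains is a differential shift. If acuity is summarised as one score that explains a share r of DAOH variance, its slope is 2.2 × sqrt(r) days per SD of the score: 0.31, 0.49, 0.70 and 0.85 days for r = 0.02, 0.05, 0.10 and 0.15. The bias in the interaction is that slope times the differential shift in SDs. The documents give no information on the size of such a shift, so these are rates per SD and not expected biases.

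**The case against.** The strongest reply is that the SAP states nothing false here. It pre-specifies a covariate list that includes diagnosis, comorbidity score and age, and its power calculation is unadjusted and claims no gain from covariates. Secondary analysis 1 uses labs and vitals for another purpose, to define a subgroup by probability of referral, so the two passages do not contradict each other. Criterion #2 also truncates each value, which limits what it can explain beyond the listed covariates. All of this stands. It sets the size of the point without removing it.

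Four stronger readings are tempting and are not supported.

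- **The omission biases the primary IV, or makes the 1.1 days wrong.** The instrument is birth-date parity. If parity is independent of acuity, the estimate is unbiased either way, and the stated figure reproduces.
- **Labs and vitals would sharpen the first stage because they predict referral.** With one as-good-as-random instrument, the large-sample standard error depends on the outcome residual, the 0.40 difference and the instrument's variance. The planned first stage is already strong: F is about 0.40²/((0.25 + 0.09)/425) = 200. In a simulation in which seven covariates strongly predicted referral but not DAOH, the SD of the IV estimate was 0.384 with and without them.
- **Any acuity difference between hospitals enters the interaction.** Only a differential change over time does. Both cohorts are described as matched, and "cohorts will be constructed using the same logic and rules", so the same ranges apply at each site.
- **The precision is free, because all seven values are certain to be on record.** The SAP does not say how a missing value is treated, and Criterion #1 read literally makes only patients with even birth dates NDC-eligible. The primary comparison is of eligible patients in both arms, which implies that Criterion #2 is applied to controls too. Some values may still be absent.

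**Conclusion.** The point holds in a limited form. For the primary IV it is an avoidable efficiency loss of unknown, possibly small size. The gain is nil if the values add nothing, about 2 power points at an assumed 5% of further variance, and about 6 at 15%. Validity is not at issue, provided that birth-date parity is independent of acuity.

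For the DiD the point concerns bias and is conditional. It matters only if acuity within the eligible ranges shifts differently at the two hospitals, net of the listed covariates. The documents neither show nor exclude such a shift. With the present list it could not be adjusted for.

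The change is worth making because the values are already needed to build the cohorts and the cost is slight. It does not follow that the primary analysis is unsound without it.

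**What to change.** Before outcomes are seen, add sodium, potassium, WBC, O2 saturation, heart rate, respiratory rate and systolic pressure to the covariate list, for both two-stage least squares stages and for the DiD.

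- Enter them as continuous terms, with a squared term where curvature is plausible.
- Take the last value recorded before the Plan to Admit order, by the same rule in both arms and at both hospitals. Criterion #2 asks for the most recent values but fixes no cut-off, and a covariate recorded later could be affected by the treatment setting.
- State in advance how an absent value is handled, by simple imputation or a missing indicator.

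If the values are left out on purpose, give the reason in the SAP.

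The cost is a few lines of SAP text, 7 to 14 degrees of freedom out of about 850, and minor missing-data handling. No enrolment or new measurement is required. The timing matters, because acuity terms added after outcomes are known would be a data-driven choice.

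### Must the referral model in secondary analysis 1 be specified further before its threshold can be called pre-specified?

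*SAP*

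**What the plan says.** In the Statistical analysis section, the first of three secondary analyses defines a subgroup by likelihood of referral: "we will use a logistic regression based on patient labs, vitals, characteristics, and comorbidities to estimate the probability of referral to NDC". The analysts will then "use a median split to define a threshold". The next sentence reads "We will then apply this threshold to the control group, and repeat the primary analysis of treatment v. control group". It ends by limiting this repeat to the high scorers in either arm: "only including patients above the pre-specified threshold".

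The same section itemises the adjustment set of the two-stage least squares model: "Covariates will include: diagnosis, comorbidity score, age, sex, insurance type, zip code, and race/ ethnicity". The referral model has no such list. Under Additional eligibility criteria specifications, Criterion #2 lists seven labs and vitals ("All of the following clinical criteria are met (using most recent labs/vitals"), but as eligibility limits and not as named predictors.

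**The concern.** A threshold is pre-specified if a reader could tell in advance which patients will fall above it. Here only the rule, a median split, is fixed. The SAP does not say outright whether the model is fitted in the encouraged arm or in both arms, which variables enter it, or whose median is taken. Different choices select different patients. If they were made with days alive and out of hospital (DAOH) in view, the subset result could depend on them even without confounding.

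There is a second worry. If the model is fitted in the encouraged arm, those patients are scored in-sample and the controls out of sample. Uptake in the encouraged upper half is then overstated, and the two halves may not be quite comparable.

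**Working it through.** **1. The plan's own figures.** The inputs are in Sample size and power: 425 per arm, two-sided 0.05, 80% power, "encouragements 50% of the time in the treatment group and there is 10% contamination in the control group", and SD 2.2 days.

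- As-randomized: (1.960 + 0.842) × √(2/425) = 0.192 SD.
- IV scale: 0.192 / (0.50 − 0.10) = 0.48 SD.
- In days: 2.2 × 0.48 = 1.056, stated as 1.1.

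These reproduce. The SAP states no figure for the subset. With about 212 per arm and the same 40-point first stage, the detectable effect would be 2.802 × √(2/212) / 0.40 = 0.68 SD, or 1.5 days.

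**2. What the text allows.**

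- *Fitting sample.* A threshold that is derived and afterwards applied to the control group was derived in the treatment group. A pooled fit and median would need no such step.
- *Whose median.* A median split halves the group that was scored. A median taken among referred patients only would keep 127-149 of 425 encouraged patients (30-35%), which is not a split into halves.
- *Who is cut.* The harmful reading would trim the controls alone. In simulation with a true effect of 0.5 day it gave mean estimates from −0.40 to −0.06 day. The SAP excludes it, because the analysis keeps only patients above the threshold.
- *Predictors.* Labs and vitals correspond plausibly to the seven in Criterion #2, and characteristics and comorbidities to the listed covariates. This mapping is an inference.

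**3. How far the open choices move the result.** Simulation: 4,000 trials per setting, 425 per arm, 50%/10% uptake, SD 2.2, no confounding, robust two-stage least squares. Assumed, not from the SAP: referral logit slope 0.8 on an index explaining 9% of DAOH variance; predictor correlation 0 or 0.3; 10 predictors (seven labs and vitals, age, sex, comorbidity score) or 17 (adding seven insurance and race/ethnicity indicators).

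| What varies | Subset changed | Shift in estimate | p<0.05 differs at 1.1 days | At least one significant, no effect |
|---|---|---|---|---|
| Treatment-arm v. pooled fit, 17 predictors | 12-14% | SD 0.20-0.24 day | 12.5-15.4% | 6.6-7.4% |
| 10 v. 17 predictors, treatment-arm fit | 11-22% | SD 0.20-0.30 day | 12.0-16.9% | 6.4-8.2% |
| All four combinations | – | median spread 0.28-0.39 day | 22.8-32.1% | 9.0-11.1% |

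The subset standard error is about 0.41-0.48 day, and any one reading rejects a true null in about 5% of trials. The last column applies only if the most favourable reading is reported.

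**4. Reading the disagreement rates.** At 1.1 days, z = 1.1/0.48 = 2.3 to 1.1/0.41 = 2.7. Power is therefore Φ(2.29 − 1.96) = 0.63 to Φ(2.68 − 1.96) = 0.76. Results this close to the cutoff change side easily. Two independent runs of one fixed analysis would disagree in 2 × 0.76 × 0.24 = 36% to 2 × 0.63 × 0.37 = 47% of trials. This is a loose benchmark, since two analyses of the same data should agree more often, and they do.

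**5. In-sample scoring.** Simulation with no true effect, 1,500 trials per setting. Bias with 17 predictors was 0.074 day under strong assumed confounding, 0.014 under weaker and 0.013 under none (Monte Carlo error 0.010-0.011). The largest is 0.074/0.41 = 0.18 standard errors. With 30 predictors and strong confounding it was 0.128 day. Rejection stayed at 4.3-5.8%. Cross-fitted scoring removes most of the bias (−0.023 to 0.000), but its standard error is 6-18% larger and its root mean squared error is 0.44-0.48 day against 0.39-0.43.

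**The case for a change.** The strongest case for a change is that the referral model decides who is analysed and yet is described less fully than the adjustment set printed just above it. Even with the treatment-arm fit granted, the predictor list alone changes significance in 12-17% of trials at 1.1 days. A longer list with 13 individual comorbidities (assumed) raises disagreement among all readings to 31-43%. In a second simulation of different design (true effect 0.5 day, unmeasured severity), the treatment-arm fit gave means of 0.52, 0.59, 0.62 and 0.71 day with 12, 20, 40 and 80 predictors. In-sample scoring therefore matters more for a long list. Naming sample and predictors would take two or three sentences.

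Part of this stands. The list is not itemised, the treatment-arm fit and its median are implied and not stated, and the word pre-specified is accurate for the rule but not for a numeric cut.

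The rest does not carry the point. The adjustment set also leaves the comorbidity index, diagnosis grouping and zip-code coding open, so the difference is one of degree. The larger disagreement figures need the pooled fit, which the wording argues against. The 10-predictor list omits insurance and race/ethnicity, which are ordinary patient characteristics. The bias requires unmeasured factors linking referral with DAOH; without them the second simulation gave 0.49 day for a true 0.5 with 40 predictors.

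**Conclusion.** No change is needed. The concern is about missing detail, not a faulty method. Referral, and not DAOH, is the outcome of this model, so sample, predictors and cut can all be settled without looking at DAOH, and the text points to one sensible version: fit and median in the treatment arm, same cut in both arms. That version keeps its error rate. Within it, the choice of predictors moves the estimate by less than its standard error. Inflation needs selection after the outcomes are seen, of which the SAP gives no sign.

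Cross-fitting would be a trade-off: a small, conditional bias exchanged for a larger mean squared error.

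The conclusion assumes a predictor list of moderate length, in line with the variables the SAP itself names; a list of 40 or more would weaken it. The simulated sizes rest on assumed coefficients and correlations, so they show that the subset result can move, not by how much it will in this trial. What is affected is one of three secondary analyses.
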